## 7.1 BASELINE/SCREENING

### 7.1.1 Within 30 days prior to registration for protocol therapy:

- Complete medical history
- Physical examination including: height, weight, BP
- ECG
- MUGA or Echocardiogram
- Adverse event and concomitant medication
- ECOG performance status

### 7.1.2 Within 14 days of registration for protocol therapy:

- Complete metabolic profile (CMP) including: serum chemistries (creatinine, glucose, total protein, blood urea nitrogen [BUN], total carbon dioxide [CO2], albumin, total bilirubin, alkaline phosphatase, and aspartate transaminase [AST] and alanine transaminase [ALT]) and electrolytes (total calcium, chloride, potassium, sodium)
- Calculated creatinine clearance
- Platelets, ANC, Hgb
- Urine pregnancy test or serum HCG (for women of child bearing potential)

## 7.2 ON TREATMENT

### 7.2.1 Day 1 of each cycle (within 3 days prior):

**Note: Cycle 1 Day 1 testing need not be repeated if completed within 7 days of starting protocol therapy.**

- Physical examination including
- weight, B/P and ECOG performance
- Platelets, ANC, Hgb
- Complete metabolic profile (CMP) including: serum chemistries (creatinine, glucose, total protein, blood urea nitrogen [BUN], total carbon dioxide [CO2], albumin, total bilirubin, alkaline phosphatase, and aspartate transaminase [AST] and alanine transaminase [ALT]) and electrolytes (total calcium, chloride, potassium, sodium)
- Calculated creatinine clearance
- ECGs will be done prior to each treatment cycle in the safety-run in cohorts and prior to cycle 3 of combined therapy in randomized portion of the study. Additional ECG monitoring should be considered at the treating physician's discretion, in patients who develop clinically significant electrolyte abnormalities
- Assessment of adverse events and concomitant medications
- PK levels: For patients enrolled in the safety-run-in portion of the study and Arm B - Mandatory plasma sample to be collected prior to infusion and 5 min (+/- 5 minutes) prior to the end of infusion on Cycle 1 Day 3 and Cycle 2 Day 3
- Optional whole blood sample (genomic DNA) to be collected on all patients at cycle 1 day1.
- Correlative studies: (See SPM for collection and shipping instructions).
  - Optional - tumor tissue submission from diagnosis

- Mandatory - tumor tissue submission from definitive surgery

### 7.3 IV MAINTENANCE THERAPY

- During maintenance therapy patient will have weekly BP and weight along with study drug
- Every 4 weeks they need:
  - Physical examination
  - ECOG Performance status
  - Platelets, ANC, Hgb
  - Complete metabolic profile (CMP) including: serum chemistries (creatinine, glucose, total protein, blood urea nitrogen [BUN], total carbon dioxide [CO2], albumin, total bilirubin, alkaline phosphatase, and aspartate transaminase [AST] and alanine transaminase [ALT]) and electrolytes (total calcium, chloride, potassium, sodium)
  - Assessment of adverse events and concomitant medications
- PK levels: Plasma to be collected prior to infusion and 5 min (+/- 5 minutes) prior to the end of infusion during Week 1 and Week 5

### 7.4 ORAL MAINTENANCE THERAPY

- During maintenance therapy patient will administer the study drug weekly. Patients should be instructed to take the drug in clinic on week 1 and week 5 so PK samples can be obtained. All other doses are self-administered at home.
- Every 4 weeks they need:
  - Physical examination
  - ECOG Performance status
  - Platelets, ANC, Hgb
  - Complete metabolic profile (CMP) including: serum chemistries (creatinine, glucose, total protein, blood urea nitrogen [BUN], total carbon dioxide [CO2], albumin, total bilirubin, alkaline phosphatase, and aspartate transaminase [AST] and alanine transaminase [ALT]) and electrolytes (total calcium, chloride, potassium, sodium)
  - Assessment of adverse events and concomitant medications
- PK levels: Plasma to be collected prior to administration and 2 hours post-dose (+/- 5 minutes) during Week 1 and Week 5 only. PK samples should be drawn during the first and fifth week of oral maintenance therapy in patients switching from the IV formulation.

### 7.5 TREATMENT DISCONTINUATION

A patient will be discontinued from the treatment under the following circumstances:

- If there is evidence of progressive disease.
- If the attending physician thinks a change of therapy would be in the best interest of the patient.
- If the patient requests discontinuation.
- If the drug(s) exhibit(s) unacceptable adverse event. Patients will be followed until the resolution of these adverse events.
- If a patient becomes pregnant.

- Patients can stop participating at any time. However, if they decide to stop participating in the study, patients will continue to be followed for progression and survival unless the patient has also withdrawn consent for further follow-up.

## 7.6 POST TREATMENT EVALUATIONS: ~30 days -60 days from last treatment

- Physical examination
- weight, BP
- ECOG performance
- Platelets, ANC, Hgb
- Complete metabolic profile (CMP) including: serum chemistries (creatinine, glucose, total protein, blood urea nitrogen [BUN], total carbon dioxide [CO2], albumin, total bilirubin, alkaline phosphatase, and aspartate transaminase [AST] and alanine transaminase [ALT]) and electrolytes (total calcium, chloride, potassium, sodium)
- Assessment of adverse events and concomitant medications

## 7.7 FOLLOW-UP:

- Patients will be monitored by their treating physicians for the development of either local (chest wall, axillary, or supraclavicular nodes) or distal recurrent disease at least once every 4 months for the first two years, then at least every 6 months during years 3-5 after randomization.
- Suggested guidelines for surveillance of breast cancer survivors are available through the National Comprehensive Cancer Network ([www.nccn.org](http://www.nccn.org)).
- Routine blood work or radiology in the absence of symptoms suggestive of recurrent disease is not recommended.
- Remaining breast tissue (contralateral breast and ipsilateral breast in patients treated with breast conserving surgery) should be imaged annually according to standard screening guidelines.

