**Randomized Phase II – Arm A**

	Screening		Cycles 1-4	Post-treatment	Follow-up
	-30 days	-14 days	D1  (+/-3 days)	30-60 days from last treatment	+/-1 month
REQUIRED ASSESSMENTS					
Medical history	X				
Height	X				
Physical examination	X		X	X	X 
BP, weight	X		X	X	X 
ECOG performance status	X		X	X	X 
Blood Chemistries 		X	X	X	
Calculated creatinine clearance		X	X	X	
Platelets, ANC & Hgb		X	X	X	
Breast imaging					yearly
Electrocardiogram 	X		X		
MUGA or Echocardiogram	X				
Urine pregnancy or serum HCG 		X			
Adverse event and concomitant medication assessment	X		X	X	
TREATMENT					
Cisplatin			X		
CORRELATIVE STUDIES					
Tumor from diagnosis -Optional	X				
Tumor from definitive surgery -Mandatory	X				
Genomic DNA - Optional			X 		

1. Screening values obtained within 7 days of Day 1 do not need to be repeated prior to cycle 1 day 1.

2. Serum chemistries (creatinine, glucose, total protein, blood urea nitrogen [BUN], total carbon dioxide [CO2], albumin, total bilirubin, alkaline phosphatase, and aspartate transaminase [AST] and alanine transaminase [ALT]) and electrolytes (total calcium, chloride, potassium, sodium).

3. ECG will be done at baseline and prior to cycle 3. Additional ECG monitoring should be considered in patients who develop clinical significant electrolyte abnormalities during cisplatin therapy at the discretion of the treating physician.

4. Only in women of child bearing potential

5. If the genomic sample collection is missed at cycle 1 day 1, it can be collected at any time point during the study.

6. Every 4 months throughout years 1-2, then every 6 months for years 3-5.

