### **12.1 Sample Size Justification**

The primary endpoint for this trial is 2 year DFS. In order to detect an improvement of the fraction of patients free from disease at 2-year from 40% in the control arm to 63.2% in the rucaparib arm (corresponding to an HR=0.5), 38 events are needed to have 80% power to detect a difference in DFS using a one-side log-rank test with 0.10 level of significance (calculation done using nQuery Advisor 7.0 and assuming exponential survival). In order to observe 38 events we need to accrue about 102 patients, with an accrual time of about 13-18 months and an overall study duration around 25-30 months. In addition, 6 patients will be needed at the lower dose (cohort 1). Assuming ~20% will not be confirmed to have TNBC on central review; the total sample size will be increased to 135 to ensure 102 in the primary analysis (using cohort 2 and the randomized patients) and 6 in the safety analysis for cohort 1.

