## 12.4 Analysis of Primary Objective

The comparison of DFS between the two groups will be made using an unstratified Kaplan-Meier analysis with a log-rank test to test for differences using the patients in safety run-in cohort 2 and the randomized portion of the study. A specific comparison of 2-year DFS will be made using a two-sample test based on the complementary log-log transformation as suggested in Klein, et al. As supportive analysis, a stratified log-rank test will be done using the stratified randomization factors neoadjuvant anthracycline versus not and lymph node involvement at time of definitive surgery versus not. In addition, sensitivity analyses using Cox regression may be carried out to identify prognostic factors and provide adjusted estimates of the treatment group differences in DFS.

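### Four-weekly examinations in Arm B during maintenance, against 4-monthly follow-up in Arm A, can date recurrences earlier in Arm B and tilt the DFS log-rank slightly against rucaparib

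*Combined protocol and SAP*

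**What the plan says.** In the Arm A schedule (section 7.0), Day 1 visits in cycles 1-4 lead to one visit 30-60 days after last treatment, then follow-up "Every 4 months throughout years 1-2, then every 6 months for years 3-5". Section 7.7 sets the same minimum for all patients, "at least once every 4 months for the first two years", and adds: "Routine blood work or radiology in the absence of symptoms suggestive of recurrent disease is not recommended". Breast imaging is yearly in both arms.

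In Arm B, maintenance starts 3 weeks after Day 1 of the last combination cycle and lasts 24 weeks (5.2.2, Tables 5 and 6). Sections 7.3 and 7.4 introduce the same clinic list for both formulations with "Every 4 weeks they need": physical examination, performance status, blood count, chemistry, adverse events and concomitant medications. Arm B then has its own post-treatment visit and the same 4-monthly follow-up.

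Section 8.0 times DFS from randomisation to the event. It accepts pathological or radiological confirmation but does not say which date counts. Section 12.4 states: "The comparison of DFS between the two groups will be made using an unstratified Kaplan-Meier analysis with a log-rank test". It adds a 2-year comparison on the complementary log-log scale, a stratified log-rank and optional Cox models. None of these addresses visit timing.

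**The concern.** Chest-wall, axillary and supraclavicular recurrences, which 7.7 names, can be found by physical examination. An abnormal safety laboratory value or a symptom reported at a visit can also prompt imaging. A patient seen every 4 weeks has more such opportunities than one seen every 4 months. If the true recurrence times are the same, recorded times will then be shorter in Arm B for events first found at visits.

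The log-rank uses the order of recorded times, so it absorbs this difference as if it were a treatment effect. The trial is powered on that test with few events, and 12.4 offers no analysis showing how much of the result depends on visit frequency. The log-rank and the 2-year comparison could also disagree somewhat for a reason unrelated to the drug.

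**Working it through.** **1. The plan's own figure.** Section 12.1: "38 events are needed to have 80% power to detect a difference in DFS using a one-side log-rank test with 0.10 level of significance", for an improvement "from 40% in the control arm to 63.2% in the rucaparib arm (corresponding to an HR=0.5". The hazard ratio is ln(0.632)/ln(0.40) = 0.501. Schoenfeld events = 4 × (1.2816 + 0.8416)² / (ln 0.5)² = 37.5, so 38, with power 80.4%. The figure is reproduced. Section 12.1 also says "In order to observe 38 events we need to accrue about 102 patients".

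**2. Visit calendars, counted from randomisation.**
- Arm A: weeks 0, 3, 6 and 9; post-treatment visit at about weeks 13-18 (taken as month 3.56); then months 4, 8, 12, 16, 20, 24.
- Arm B: weeks 0, 3, 6 and 9; 4-weekly from week 12 to week 36 (months 2.76, 3.68, 4.60, 5.52, 6.44, 7.36, 8.28); post-treatment visit at about month 9.52; then months 12, 16, 20, 24.

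Between months 4 and 9, Arm B has five examinations (weeks 20, 24, 28, 32, 36). Arm A has one at month 8, plus one on the boundary at month 4.

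**3. Detection delay for a visit-detected event.** The mean delay is about half the gap between visits. In Arm A, 4 months = 17.4 weeks, and half is 8.7 weeks. In Arm B, half of 4 weeks is 2.0 weeks. Over the whole window from about month 3.5 to 9.5, the simulated means are 2.2 and 0.5 months, a difference of 1.7.

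**4. Apparent DFS at equal true hazard, if every event is found at a visit.** The control hazard is −ln(0.40)/24 = 0.0382 per month and S(m) = exp(−0.0382 m). Apparent DFS at month m equals true S at the last visit up to m.

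| Month | Arm A calendar | Arm B calendar | Gap |
|---|---|---|---|
| 6 (true 79.5%) | S(4) = 85.8% | S(5.52) = 81.0% | 4.8 points |
| 7.5 | S(4) = 85.8% | S(7.36) = 75.5% | 10.3 points |
| 12 | 63.2% | 63.2% | 0 |
| 24 | 40.0% | 40.0% | 0 |

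The window holds (S(3.56) − S(9.6))/(1 − 0.40) = (0.873 − 0.693)/0.60 = 30% of control events expected by 2 years.

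**5. Effect on the log-rank (simulation).** Assumptions: 51 per arm (equal allocation is implied by 12.3), exponential times unless noted, and accrual and total duration within 12.1's ranges. The share found at visits is assumed, because the documents do not give it. Ranges are results from separate runs.

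| Accrual / total (months) | Share at visits | HR under no effect | Rejection for rucaparib (nominal 10%) | Power at HR 0.5: protocol visits vs equal visits |
|---|---|---|---|---|
| 18 / 30 | 25% | 1.008 | not tabulated | not tabulated |
| 18 / 30 | 50% | 1.015 | 9.1% | 81.9% vs 82.8% |
| 18 / 30 | 100% | 1.02-1.03 | 7.5-8.9% | 80.3% vs 81.5% |
| 15.5 / 27.5 | 50% | 1.01-1.02 | 9.0% | loss about 1 point |
| 15.5 / 27.5 | 100% | 1.03-1.05 | 7.1-8.9% | 77-78.7% vs 80.9% |
| 18 / 30, hazard peaking in months 3-10 | 100% | 1.06 | 6.6% | 81.7% vs 85.0% |

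The 77% comes from a small run (1,500 trials, error about 1.1 points) and gives the largest loss: 80.9 − 77 = 3.9 points.

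**6. Dependence on the visit clock.** If sites instead counted the 4 months from end of treatment, with every event found at a visit, apparent DFS at equal hazard would favour Arm B. At 12 months it would be S(9.52) = 69.5% against S(11.56) = 64.3%. At 24 months it would be S(21.52) = 44.0% against S(23.56) = 40.7%.

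**7. Testing the remedy.** The schedule allows ±1 month on follow-up visits. Results with that window (2,500 trials per case):
- Actual dates: HR 1.02 under no effect, power 78.5%.
- Each event rounded up to the next 4-month point: HR 1.035, power 74.2%. A month-8 visit held late is pushed to month 12.
- Each event assigned to its nominal scheduled visit: HR 0.99, power 81.8%.

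**The case against.** The strongest reply is that the extra Arm B visits are safety visits. They add no imaging and no formal recurrence assessment. In 7.7 the 4-month interval is a minimum, radiology is driven by symptoms in both arms, and yearly breast imaging is common to both. Many recurrences will surface through symptoms between visits, and for those the calendars do not matter. The error is also conservative for the log-rank: it makes a false claim of benefit less likely. The named endpoint is 2-year DFS, and 12.4 already has a comparison at that point. All of this stands, and it is why the effect is small. It does not remove the point, because 12.1 bases power on the log-rank and nothing in 8.0 or 12.4 handles visit timing.

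A reader might go further in four ways that the documents do not support:
- *Recurrences are systematically dated earlier in Arm B.* This can happen only for events first found at a scheduled visit, and that share is unknown.
- *Arm B's monthly bloods contradict 7.7.* That advice concerns surveillance during follow-up. The maintenance bloods are on-treatment safety tests.
- *The follow-up clock is undefined.* The schedule footnotes give no anchor, but 7.7 ends by referring to time after randomisation.
- *A common-grid analysis should decide the result if it differs from the primary test.* Nothing here justifies a supportive analysis overriding the pre-specified one.

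**Conclusion.** The point holds as a minor one. The unequal examination schedule is in the protocol, and the plan has no analysis that allows for it. Its direction on the log-rank is against rucaparib when visits are counted from randomisation. Assuming 50-100% of events are first found at visits, the hazard ratio under no effect is about 1.01-1.05 and the power loss about 1-4 points. It reaches 1.06 only if every event is found at a visit and the hazard also peaks during maintenance. If a quarter are found at visits, the shift is under 1%. The required 38 events do not change.

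The fixed 1- and 2-year comparisons are largely spared, because both arms have visits at months 12 and 24. A reader might infer that the primary comparison is seriously compromised, or that the design needs more visits in Arm A. The figures support neither.

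**What to change.** In 12.4, add one pre-specified supportive DFS analysis, applied identically in both arms:
- Assign each non-fatal event to the nominal 4-month follow-up visit at which it was found, even if that visit was held early or late within its window.
- Assign events found at an Arm B maintenance visit, and events found between visits, to the next nominal 4-month visit.
- Use the date of first suspicion, not of confirmation. With visits on time and an assumed mean 2-week confirmation delay, rounding up to the next grid point gave HR 1.05 under no effect and 75% power.
- Keep deaths on their actual dates.
- Use a log-rank suited to heavy ties. An interval-censored analysis is an equivalent alternative.
- Count time for cohort 2 patients from registration, since they are in the primary analysis but were not randomised.

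Report it beside the primary log-rank, without overriding it. The cost is one extra analysis with coarser event times. It adds no visits and does not change the sample size.

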## 8.0 CRITERIA FOR DISEASE EVALUATION

The primary efficacy endpoint of this trial is disease-free survival (DFS) in patients confirmed (by central testing) to have triple negative tumors or known BRCA1/2 mutation. DFS is defined as the duration of time from randomization to time of an DFS event, defined as local failure (invasive), regional failure, distant failure, contralateral breast cancer (invasive or non-invasive), any other second cancer (excluding non-melanomatous skin cancer or cervical cancer in situ), or death from any cause. The diagnosis of local or distant recurrence *should ideally be pathologically confirmed*, however if biopsy if not possible, radiology confirmation by CT, MRI, or PET scan is acceptable.

## 9.0 BIOLOGICAL CORRELATIVES

### 9.1 Central Pathology Reassessment

Analysis by an American Society of Clinical Oncology (ASCO) and College of American Pathology (CAP) expert panel suggests that approximately 20% of ER, PR, and HER2 tests performed in community laboratories are inaccurate with a fairly equal distribution of false positive and false negative results. While the ASCO/CAP guidelines seek to improve test quality and reliability, the impact of these recently published guidelines is not yet fully known. As such, a retrospective central reassessment of histological subtype, tumor grade, ER, PR, and HER2 will be performed by [name] for quality assurance and to confirm tumor phenotype. Tissue Microarrays (TMA) will be constructed to facilitate potential future correlative studies including genetic assessment of DNA damage repair pathways and potential gene expression profiles that might predict sensitivity to PARP inhibition.

Formalin-fixed paraffin-embedded (FFPE) tissue from biopsy at the time of initial diagnosis (optional) and from the residual disease removed at the time of definitive surgery (mandatory) should be sent within 30 days of randomization (or registration for patients enrolled to the safety run-in).

**NOTE:** Patients will be asked to consent to allow banking of their tumor samples for future correlative studies. Only tumor samples from consenting patients will be included in the TMAs.

Detailed instructions on sample collection, processing and shipping are outlined in the Study Procedures Manual.

### 9.2 Genomic DNA – Optional

It has become increasingly clear that therapeutic heterogeneity may arise from differences in the tumor (e.g. p53 expression or defects in DNA repair) and/or differences in the host (e.g. single nucleotide polymorphisms). Although a candidate gene approach is a high yield strategy for biomarker discovery, the variability seen in most disease processes is highly dependent on complex gene-gene interactions. Recently, advances in technical platforms and bioinformatics have made genome wide association studies (GWAS) feasible. This comprehensive approach has led to some important discoveries including identification of genes, SNPs, and haplotypes associated with breast cancer, lung cancer, colon cancer, prostate cancer, myocardial infarction, and type-2 diabetes. Thus, GWAS has become a powerful platform for biomarker discovery. DNA samples from patients enrolled in this trial will be an incredibly valuable resource for potential future correlative studies using these emerging genomic and pharmacogenomic technologies.

Whole blood will be collected for assessment of potential genomic determinants of response and toxicity.

**NOTE:** Patients will be asked to consent to allow banking of their DNA for future correlative studies. Only whole blood samples from consenting patients should be submitted.

Detailed instructions on sample collection, processing and shipping are outlined in the Study Procedures Manual.

### **9.3 Rucaparib Pharmacokinetics (Safety Run-in Cohorts and Arm B patients only) – Mandatory**

Extensive pharmacokinetics (PK) is being conducted in several ongoing rucaparib trials and thus detailed PK sampling is not planned in this trial. However, limited PK sampling will be conducted to complement the other ongoing efforts. Plasma samples will be obtained prior to infusion and 5minutes (+/- 5 minutes) prior to the end of infusion on Day 3 of cycles 1 and 2 during combination therapy and weeks 1 and 5 of IV maintenance therapy. Plasma samples will be obtained prior to administration and 2 hours (+/- 5 minutes) post dose during week 1 and week 5 of oral maintenance therapy in all patients (including those who initiated maintenance therapy with the IV formulation). For all collections, the start and end of rucaparib infusion as well as actual time of all PK sample collections should be recorded in the source documents. PK samples will be assayed for rucaparib (CO-338/AG-014699/PF-01367388) using a validated analytical method. Detailed instructions on sample collection, processing and shipping are outlined in the Study Procedures Manual.

